4.5 STUDY ASSESSMENTS

Case-Cohort:

Self-completed, offered online (can be offered by phone/on paper for participants who request this).

1. Demographics
2. Questionnaires (in order of priority)
 - a. Wellcome Trust COVID 19 questionnaire (Most up to date version in use at the time of the study): This is a comprehensive instrument covering physical, cognitive, and mental health domains and will also allow comparison to developing UK reference population data). Questions deemed to require additional support have been removed.
 - b. Diabetes Related Quality of Life (DQOL)

- c. Diabetes-Specific [name]-1
 - d. EQ5D
3. Option to self-nominate for nested case control study.

Nested Case Control (CRF visit):

1. Written consent
2. Questionnaires (if not done previously) or Update of symptoms score Wellcome questionnaire section 1.3
3. Blood sample (optional) for research labs (16ml total, 6ml purple top (EDTA), 6ml gold top (serum), 4ml blue top (citrate)) for non-routine bloods: inflammatory (e.g. CRP), vascular (t-PA, vWF) and cardiac (hs troponin, NT proBNP) biomarkers consistently predictive of long-term adverse outcomes.
4. Blood sample (8ml total, 3ml purple top (EDTA) and 5ml gold top (serum)) for routine clinical measures (HbA1c, LFTs, lipids, U&Es).
5. Physical measures
 - a. Incremental walking test
 - b. Grip strength
6. Waist and thigh measurement
7. Bioimpedance (optional if site does not have this equipment)
8. Pulmonary function test (optional if site does not have this equipment)

Cases will be invited to a repeat study visit 1 year (40 to 64 weeks) from the initial study visit.

SOPs (shared from other studies) will be used to standardise:

- Incremental walk test
- Grip strength test
- Blood sampling, storage and shipment
- Pulmonary function test

Clinical data: Baseline and follow up data from SCI-Diabetes including glucose control and blood pressure.

4.6 STUDY SAFETY ASSESSMENTS

There are no measures that will be used to evaluate or determine subject safety during the study.

Remote implied consent and Questionnaires: As these are participant facing questionnaires completed online or on paper at a time and place suitable for the participant, safety assessments are not required as there is no risk of harm to the participant.

Study visit attendees: As this is a non-interventional study with low risk of harm to participants, adverse events will not be recorded unless these relate specifically to study related tests or the study visit.

4.7 INCIDENTAL FINDINGS

Any incidental findings (previously undiagnosed condition) considered to be clinically significant will be reported to the participant's GP and/or consultant by the CI or Site PI, with the consent of the participant. However, it is not anticipated that any incidental findings will be found during the planned research.

4.8 STUDY POPULATION

The population being studied is patients with diabetes who live in Scotland and are part of the SCI Diabetes electronic medical record system.

4.9 NUMBER OF PARTICIPANTS

The total number of participants required to complete the study is 500 cases and 500 age and sex matched controls in the nested case control study. This total number may be smaller or larger, depending upon the number of COVID-19 infections which have occurred in the population with diabetes during the timeframe of the study. Reasonable efforts will be made to enrol a matched control for each case participant who is willing to attend. Multiple controls may be enrolled if the first assigned control fails to complete all aspects of the study or is re-assigned as a case.

4.10 INCLUSION CRITERIA

Case cohort study (online questionnaires):

- Person with Diabetes (Type 1 or Type 2)
- Aged 18 or over
- Able to read and write in English

Nested case control study (CRF visits):

- Cases defined by positive COVID test in the clinical record. Cases will be invited sequentially from the cohort but will be selected to include at least 200 people in each of the diabetes subgroups (type 1 diabetes or type 2 diabetes).
- Controls defined by no positive COVID test in clinical records and no reported infection by participant. Controls will be matched after matching of a limited demographic panel available from the panel (age in 5 year bands, ethnicity, sex, type of diabetes, SIMD quintile).

All participants attending a research facility must have completed a COVID safety check before attending in person, in line with local guidance. Cases will be post-COVID and at least 10 weeks post positive test result.

4.11 EXCLUSION CRITERIA

Nested case control study only:

- Participating in the intervention phase of another clinical study

Individuals will not be enrolled to the nested case control study if they are participating in the clinical phase of another interventional study or have done so within the last 30 days. Individuals who are participating in the follow-up phase of another interventional study, or who are enrolled in an observational study, will be co-enrolled where the CIs of each study agree that it is appropriate. Potential participants can choose to delay taking part until the other interventional study has been completed.

5 PARTICIPANT SELECTION AND ENROLMENT

5.1 IDENTIFYING PARTICIPANTS

Case Cohort: To allow as wide participation as possible, study instruments (questionnaires) will by default be offered remotely using an online implied consent and completion. For this

reason, we will include only contact details (e mail and or telephone) and limited, broad demographics (age in 5 year categories, ethnicity, sex, type of diabetes, duration of diabetes in 5 year categories, first 4 characters of post code). To be inclusive we will offer support for completion of questionnaires if remote online completion by the participant is not possible.

Nested Case control: This will be with written consent and include CRF visit, physical measures and data linkage to the clinical record for evidence of diabetes complications (current and future).

Case Cohort recruitment:

1. **From Diabetes Research Register:** We will utilise the NHS Research Scotland (NRS) Diabetes Research Network permission to contact research register of people with who have expressed a willingness to be involved in research. This register has a large cohort of people with diabetes (>14,000) who have given permission to be approached directly via email or letter or phone. People with diabetes in Scotland who are part of this system will be approached via email or letter or phone to take part. Remote participation does not require the R&D department permission of the Health Boards as no facility use is taking place. Within the data collected participants will be asked if they have had a positive COVID test or believe that they have had COVID infection.
2. **From diabetes clinic lists or database search (SCI Diabetes):** To augment recruitment of COVID test positive participants we will also screen clinic lists and recruit directly. A member of the study team will screen diabetes clinic lists (eg trak or local clinical system, when possible SCI Diabetes) which routinely have a note of previous COVID infection. Name and CHI noted on screening log (excel spreadsheet held on NHS computer). If patient declines this is noted and no further action. If patient assents to contact then contact information taken (telephone and email – if neither possible postal address) and added to screening log. Electronic data collection link sent by preferred means. If electronic remote data collection not possible then paper questionnaires will be made available by post or study team will discuss over the phone. Cases identified to by SCI Diabetes search will be approached in writing with Caldicott Guardian approval in place within a Health Board (likely to be used in selected Health Boards only).
3. We will also advertise the study by leaflets and posters and via newsfeed to My Diabetes My Way, allowing self-referral to the study team.

NESTED CASE-CONTROL RECRUITMENT:

Cases, by definition, will have had a positive COVID test present on the clinical record. Potential cases will be selected from the cohort where a record of self-reported COVID infection is presented. Potential cases will be invited to CRF visit by telephone or email. Where assent is given by phone the clinical record will be checked to confirm positive COVID test, visit is arranged, and PIS sent. All other study procedures will take place only after face-to-face written consent is obtained at the CRF visit.

Controls will be selected from the pool of people who have completed the online questionnaire information and who have indicated that they have not had a **positive** COVID test and do not believe that they have had COVID infection. Those who had possible infection but subsequent test negative are included. Matching will be by age (5 year category),

ethnicity, sex, SIMD quintile and type of diabetes included in the participant completed questionnaire.

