4.2 STUDY DESCRIPTION

We will recruit a large Case-Cohort of people with type 1 and type 2 diabetes in Scotland to assess the prevalence of symptoms after self-reported COVID infection. We will further recruit a nested case control study of those with positive COVID test in the clinical record (cases) and controls to examine physical measures, glycaemia and diabetes complications.

[figure not shown]
The cohort will be recruited predominantly from the NHS Research Scotland Diabetes Research Register with additional direct recruitment invited from clinic lists of those with previous evidence of COVID infection. This cohort will involve self-completed questionnaires and minimal personal information limited to contact details (e-mail, telephone) and not including patient identifiers such as name, address or CHI. The cohort will acknowledge “By ticking this box, you acknowledge that you have read the PIS and have had the opportunity to ask any and all questions to a research staff member” electronic checkbox prior to completion of demographic information and questionnaires.

The Nested Case Control study will be conducted in person under written consent and include:

[figure not shown]
- Blood sampling (for biomarkers and routine clinical measurements)
- Physical tests (incremental walk test, grip strength test)
- Waist and thigh measurement
- Bioimpedance measurement
- Pulmonary function test

Cases will repeat the CRF study visit approximately 1 year from the baseline visit.

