7.2 PROPOSED ANALYSES

An analysis plan will be prepared for the University of Glasgow Research Data Management department before the study closes, to detail what analysis will be performed on the data.

Case cohort study:

This includes **participant completed questionnaires only**. We will not have access to clinical record for whole group (limited to those in nested study) and will rely on patient self-report of COVID testing and infection to create groups. Analysis will be in three groups:

- a. Test positive COVID declared (**cohort A**)
- b. no test but self-declared COVID (**cohort B**)
- c. no COVID infection declared, including those with suspected infection but test negative (**control**)

Analysis of this data will include

1. **Frequency of COVID symptoms** (derived from question 1.3 Wellcome questionnaire: 28 domains answering yes/no for 0-28 score and by self-report at time of infection at 3 months and current (>3 months)).
 - a. **Primary analysis:** current score cohort vs control with adjustment for limited demographic panel: age band, ethnicity, sex, type of diabetes
 - b. Secondary analyses:
 - i. within cohort comparison of time of infection vs 3 months vs current
 - ii. comparison time of infection and 3 months vs current score of control (with adjustment)
2. **Other questionnaire data:** diabetes depression score, DQOL all of which are assessed currently only and will be assessed in cohort vs control.
3. Comparison of above end points in cohort B to cohort and controls.

NESTED CASE CONTROL STUDY

For this data, consent will allow access to confirm that patient is COVID test positive in the clinical record. Definitions and comparison will therefore be between:

Cases - COVID test positive in clinical record

Control - no previous clinical COVID infection reported by patient, no record positive COVID test.

Case vs control (First visit)

1. **Frequency of COVID symptoms** (derived from question 1.3 Wellcome questionnaire: 28 domains answering yes/no for 0-28 score and by self-report at time of infection at 3 months and current (>3 months)).
 - a. **Primary analysis:** current score case vs control with adjustment for age, sex, ethnicity, sex, type of diabetes, SIMD
 - b. Secondary analyses:
 - i. within cohort comparison of time of infection vs 3 months vs current
 - ii. comparison time of infection and 3 months vs current score of control (with adjustment)
 - iii. relationship of cycle threshold to symptom scores

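### One recruitment route is aimed only at COVID-positive people and is not recorded in the cohort data, so part of the case-control difference may reflect recruitment source, which the stated adjustment cannot remove

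*Protocol*

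**What the plan says.** Protocol section 5.1 gives three ways into the questionnaire cohort.

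- **Research register.** People "who have expressed a willingness to be involved in research" are invited, infected or not.
- **Clinic lists and SCI Diabetes search.** "To augment recruitment of COVID test positive participants we will also screen clinic lists and recruit directly". Section 4.2 describes the same route as "additional direct recruitment invited from clinic lists of those with previous evidence of COVID infection". For the record search, section 5.1 says "Cases identified to by SCI Diabetes search will be approached in writing".
- **Self-referral.** "We will also advertise the study by leaflets and posters and via newsfeed to My Diabetes My Way, allowing self-referral". This is open to both groups.

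Nested cases come out of that cohort: "Potential cases will be selected from the cohort where a record of self-reported COVID infection is presented". So do controls: "Controls will be selected from the pool of people who have completed the online questionnaire information", provided they report no positive test and no believed infection.

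Matching in the nested study uses age band, ethnicity, sex, SIMD quintile and type of diabetes (sections 4.10 and 5.1). The cohort primary analysis in section 7.2 is "current score cohort vs control with adjustment for limited demographic panel", namely age band, ethnicity, sex and type of diabetes. The nested primary analysis adds SIMD. Section 6.2 lists the cohort data held in RedCap, and recruitment route is not among them. Screening logs are kept apart, on NHS computers.

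**The concern.** The register and self-referral routes can supply both cases and controls. The clinic-list and record-search route is filtered on evidence of infection, so by design it supplies cases. Patients approached from clinic lists may differ from research volunteers in complications, disease severity and symptom burden whether or not they ever had COVID. Section 2 of the protocol itself says that diabetes and its complications affect wellbeing and go with depression and distress, which is why it wants controls with diabetes.

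If the two sources differ in this way, the difference is carried into the case-control contrast and would be read as an effect of COVID. Both primary comparisons are exposed, because clinic-list cases enter the cohort and can then be chosen for the nested study. The quality-of-life, walk, grip and lung function comparisons are exposed too. None of the planned covariates measures clinic attendance, severity or willingness to join research. For the questionnaire cohort as a whole, section 7.2 says there will be no clinical record from which to adjust.

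**Working it through.** **1. The plan's own figures (section 7.1).** With a two-sided 5% test (sidedness is not stated, so assumed) and 90% power, n per group = 2(1.960 + 1.282)²/d².

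- d = 0.2: 525.4, so 526, as stated.
- d = 0.5: 84.1, so 85, as stated.
- At the planned 500 per group, SE = √(2/500) = 0.0632 SD and power for 0.2 SD is 88.5%.

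These figures are correct and are used below only as a scale.

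**2. Which routes supply which group.**

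| Route (section 5.1) | Cases | Controls |
|---|---|---|
| Research register | yes | yes |
| Clinic lists, SCI Diabetes search | yes | none by design |
| Self-referral | yes | yes |

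A covariate for route estimates the COVID effect within each route. In the second row there is nobody, or almost nobody, to compare the cases with, so those cases would add essentially nothing to an adjusted contrast.

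**3. Size of the possible bias.** Let f be the share of cases from the second route and s the difference in symptom score between sources, in SD units, that remains after the planned adjustment. Then bias = f × s. The protocol gives neither f nor s, so both are assumed. The rejection rate is that of a nominal two-sided 5% test at 500 v 500 when COVID has no effect.

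| f | s (SD) | Bias (SD) | Share of 0.2 SD target | Rejection rate |
|---|---|---|---|---|
| 20% | 0.2 | 0.04 | 20% | 9.7% |
| 25% | 0.2 | 0.05 | 25% | 12.4% |
| 50% | 0.2 | 0.10 | 50% | 35% |
| 50% | 0.3 | 0.15 | 75% | 66% |

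Outside that range, f = 10% with s = 0.2 gives 0.02 SD and 6.2%. If s = 0 there is no bias at all. If clinic-list patients have fewer symptoms than volunteers, the sign reverses and a real effect would be understated.

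**4. Precision of a contrast restricted to shared routes.** With f between 20% and 50%, 400 to 250 of the 500 cases remain. SE = √(1/n_cases + 1/n_controls).

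| Cases v controls | SE (SD) | Power for 0.2 SD |
|---|---|---|
| 400 v 500 | 0.0671 | 85% |
| 250 v 500 | 0.0775 | 73% |
| 400 v 400 (matched pairs kept) | 0.0707 | 81% |
| 250 v 250 (matched pairs kept) | 0.0894 | 61% |

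The pair-kept rows use the two-sample formula and credit no gain from matching. Section 12.3 allows the study to end with 100 cases. With half of them from clinic lists, 50 v 50 has SE 0.200 SD and about 17% power.

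**5. Can route be recovered later?** For nested participants, in part: the screening log holds CHI for clinic-list approaches, and a file linking CHI to study ID is made after written consent (sections 5.1 and 6.2). For people who only complete the questionnaire, no reliable link is described: no CHI is held, contact details are optional, and section 6.1 treats the data as anonymous.

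**The case against.** A reader might infer that part of the observed difference is a source artefact, or that the 66% rejection rate describes this study. The documents support neither. They give no share of cases by route and no symptom difference between routes. Section 4.2 says the cohort comes mainly from the register, and section 4.8 places the whole study population in SCI Diabetes, so register volunteers may attend the same clinics. The matching narrows any gap further. A clinic-list invitee who denies infection could in principle become a control. This stands: the bias is possible, not shown.

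It is also fair that a sensitivity analysis by source is ordinary content for an analysis plan, which section 7.2 promises. But section 7.2 already fixes the covariates, and an analysis plan written before the study closes cannot use a route that was never recorded for the questionnaire cohort. The recording gap belongs to the protocol.

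For the nested study the objection has more force. Clinic-list route can be traced there, and linked HbA1c, complications and admissions allow severity to be examined.

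Finally, the stated primary objective is the proportion of infected people with longer-term symptoms. Wider case recruitment may serve that better than volunteers alone. This is a reason to keep the clinic-list cases in the study. It does not justify comparing them with controls from other sources as if source did not matter.

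**Conclusion.** The point holds as a possible bias that the plan neither measures nor guards against. One recruitment route is selected on infection and has no counterpart for controls, the matching and adjustment omit source, and the cohort dataset does not record it. Under the assumed 20-50% share and 0.2-0.3 SD residual source difference, the bias is 0.04-0.15 SD, a fifth to three quarters of the design target. Those inputs are not in the protocol, and neither the size nor the direction can be derived from it.

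Restricting to shared routes removes only the cases-only-route problem. It would not make the contrast unbiased in general, since infected people with symptoms may answer a volunteer invitation more readily. This is a low-cost improvement and does not invalidate the study.

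**What to change.** 1. Add a recruitment-route field (register, clinic list or record search, self-referral) to the RedCap cohort data in section 6.2, for example through a separate link per route. For nested participants already enrolled, trace clinic-list route through the screening log and the file linking CHI to study ID.
2. In section 7.2, pre-specify for the cohort and nested primary analyses a contrast restricted to register and self-referred participants on both sides, adjusted for route, and report it beside the all-route contrast. State in advance whether the nested version keeps matched pairs or keeps all controls with covariate adjustment.
3. State in advance that any discrepancy between the two will be reported as a limit on attributing the difference to COVID. Do not choose the headline result after seeing both.
4. Keep clinic-list cases for the prevalence estimate, the description of symptoms within cases and the one-year follow-up.

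The cost is one field and one extra run per primary analysis, with no new recruitment. The restricted contrast is less precise, as shown in the working, and would be weak if the study closed near its 100-case minimum.

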12.3 END OF STUDY	20
13 REPORTING, PUBLICATIONS AND NOTIFICATION OF RESULTS.....	21
13.1 AUTHORSHIP POLICY	21
13.2 PUBLICATION.....	21
13.3 PEER REVIEW.....	21
14 REFERENCES.....	21

PROTOCOL APPROVAL

Longer term impact of COVID 19 infection in people with diabetes

Signatures

The undersigned confirm that the following protocol has been agreed and approved by the Sponsor and that the Chief Investigator agrees to conduct the study in compliance with this approved protocol and will adhere to the principles of GCP, the Sponsor SOPs, and any other applicable regulatory requirements as may be amended from time to time.

[name]
Chief Investigator

Signature

Date

[INSERT PI NAME]
[INSERT HEALTH BOARD
SITE NAME]
Principal Investigator

Signature

Date

LIST OF ABBREVIATIONS

AE	Adverse Event
BG	Blood Glucose
CI	Chief Investigator
CNORIS	Clinical Negligence and Other Risks Indemnity Scheme
COVID-19	Coronavirus SARSCOV-2
CRF	Clinical Research Facility
DMS	Data Management System
GCP	Good Clinical Practice
ICF	Informed Consent Form
NHS GGC	NHS Greater Glasgow and Clyde
ISF	Investigator Site File
NRS	NHS Research Scotland
PI	Principal Investigator
REC	Research Ethics Committee
SDG	Scottish Diabetes Group
SOP	Standard Operating Procedures
SMF	Study Master File

SUMMARY/SYNOPSIS

Study Title	Longer term impact of COVID 19 infection in people with diabetes (Short Title: Diabetes Long COVID study)	
Study Design	Observational Case Cohort study with Nested Case Control study	
Study Population	Adults with Type 1 and Type 2 Diabetes in Scotland	
Sample Size	Total sample size in Nested Case Control study, as per IRAS form: 1000 participants (500 cases and 500 matched controls, with at least 200 people in each of the categories of Type 1 and Type 2 diabetes)	
Planned Study Period	May 2021 to approximately October 2022	
Follow up phase duration	1 year (cases only)	
Aims	To understand the proportion of people with diabetes who experience longer term symptoms or illness after covid-19 infection, the nature of these symptoms, and the potential health impact of that.	
Primary	Objective: Case Cohort: After COVID infection, what proportion of people with type 1 and type 2 diabetes experience symptoms in the longer term (up to 18-24 months after index infection)?	Outcome Measures: The prevalence of symptoms in the longer term in people with diabetes up to 2 years after COVID-19 infection using Wellcome questionnaire

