6.2 DATA MANAGEMENT SYSTEM

We will use the RedCap data management system (DMS) hosted on a secure server at The University of Glasgow. This system will host all study information with the exception of screening logs and secure link between patient identifiers and study ID - both of which will be held separately on NHS computers. The RedCap platform allows for direct data entry by participants using either personal computer or smartphone.

Data held in NHS – on secure computer in CRF at each recruiting site:

Screening log for invitation to cohort from clinic lists – this will include patient identifiers restricted to CHI, name, telephone number, email address, as well as study process details (date contacted, consent given to send link for questionnaire data).

After written consent a separate file will be maintained with CHI and study ID.

Data held in RedCap (University of Glasgow)

All Cohort study information. This is entered by the participant and includes:

1. Panel of limited demographics (age in 5 year categories, ethnicity, sex, type of diabetes, duration of diabetes in 5 year categories, first 4 characters of post code to allow calculation of SIMD quintile)
2. Contact details (telephone, email address) – optional for participant
3. Study questionnaires (Wellcome, DQOL, DDS-1, EQ5D)

For nested case control study to this will be added:

1. Nested case control screening information recording interest in study/ willingness to attend CRF

After written consent at CRF the following will be added:

2. study ID
3. completed data from CRF visit (incremental walking, hand grip, pulmonary function, waist and thigh measurement, bioimpedence)
4. Participant information including (age to nearest year, ethnicity, sex, type of diabetes, diabetes duration), **e-mail address and/or contact telephone number**
5. Self filled questionnaire
6. Electronic pseudonymised linkage to variables in electronic clinical record being

- a. Sci-diabetes with measures of glycaemia (HbA1c), nephropathy, retinopathy, foot disease
 - b. SMR01 with data on hospital admissions
 - c. Where possible COVID test data for positivity and cycle threshold (cT)
- 7.

The DMS will be based on the protocol and case report form for the study and individual requirements of the investigators. The case report form will collect only information that is required to meet the aims of the study and to ensure the eligibility and safety of the participant.

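### The primary symptom prevalence pools self-referrers to an advertised Long COVID study with invited people, and the listed cohort data hold no recruitment route, so the resulting selection bias could not be assessed

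*Protocol*

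**What the plan says.** The Synopsis gives the primary outcome as "The prevalence of symptoms in the longer term in people with diabetes up to 2 years after COVID-19 infection using Wellcome questionnaire", and section 3 states the primary objective as a proportion among people who have had COVID. The Synopsis also gives the name under which the study runs: "Short Title: Diabetes Long COVID study".

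There are three ways into the online cohort.

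- Register: section 4.2 says "The cohort will be recruited predominantly from the NHS Research Scotland Diabetes Research Register".
- Clinic lists or a SCI Diabetes search (5.1): "To augment recruitment of COVID test positive participants we will also screen clinic lists and recruit directly".
- Advertising (5.1): "We will also advertise the study by leaflets and posters and via newsfeed to My Diabetes My Way, allowing self-referral to the study team".

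On stored data, section 5.1 says that, besides the questionnaires, "we will include only contact details (e mail and or telephone) and limited, broad demographics". Section 6.2 lists the cohort items held in RedCap. The first is "Panel of limited demographics (age in 5 year categories, ethnicity, sex, type of diabetes, duration of diabetes in 5 year categories", together with part of the post code; optional contact details and the questionnaires follow. Recruitment route is not in the list. The only record tied to a route is the "Screening log for invitation to cohort from clinic lists", which is kept on NHS computers outside RedCap.

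Section 7.2 forms the cohort groups from what participants report about COVID testing and infection. It adjusts the primary comparison for age band, ethnicity, sex and type of diabetes.

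**The concern.** A proportion depends directly on who enters its denominator. The register and list routes start from people who can be counted before they are approached, so a response rate can be reported. The advert route has no such starting list. People with lingering symptoms plausibly have more reason than recovered people to answer an advert for a study named after Long COVID.

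The control group does not repair this. It can help a comparison of scores, but the absolute prevalence among infected people has no comparator to absorb the selection. The absolute level matters here because it is the stated primary outcome, and because sections 2 and 4.5 intend comparison with other populations.

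The gap lies in data capture, so it cannot be left to a later analysis plan. Section 7.2 requires that plan only before the study closes, when most responses may already be in. If route is not stored as people enter, the listed items offer no way to reconstruct it.

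**Working it through.** **Can route be recovered later?** Set side by side, the protocol's provisions suggest not.

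- The study matrix (4.4) shows the cohort questionnaire as a single completion at any time.
- Contact details are optional (6.2), and 6.1 describes the questionnaire data as anonymous.
- The clinic-list log is separate from RedCap. The file joining CHI to study ID is created only after written consent, that is, for the nested study (6.2).
- Even a linked log would identify only clinic-list invitees. It would not separate self-referrers from register respondents.

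**How large could the effect be?** The protocol gives no figure for this bias, so there is none to reproduce. The sample sizes in 7.1 (526 and 85 per group) do reproduce, but they concern differences between two groups and do not bear on the point.

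Inputs, all assumed except the first:

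- p = 0.55, prevalence among COVID cases who did not self-refer. This is the early estimate quoted in 7.1, used here only as a working value.
- r = 1.5, 2 or 4: how many times as likely a person with symptoms is to self-refer as one without.
- f = 5%, 20% or 50%: self-referrers' share of the COVID cohort.

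Prevalence among self-referrers is ps = r·p / (r·p + 1 − p):

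- r = 1.5: 0.825 / 1.275 = 64.7%
- r = 2: 1.10 / 1.55 = 71.0%
- r = 4: 2.20 / 2.65 = 83.0%

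Pooled prevalence is (1 − f)·p + f·ps, with the shift in points in brackets:

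| f | r = 1.5 | r = 2 | r = 4 |
|---|---|---|---|
| 5% | 55.5% (+0.5) | 55.8% (+0.8) | 56.4% (+1.4) |
| 20% | 56.9% (+1.9) | 58.2% (+3.2) | 60.6% (+5.6) |
| 50% | 59.9% (+4.9) | 63.0% (+8.0) | 69.0% (+14.0) |

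At r = 1 the shift is zero for any f. With p = 0.40 instead, r = 2 and f of 10% to 30%, the pooled figure is 41.7% to 45.1%, a shift of 1.7 to 5.1 points.

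**Against sampling error.** At n = 500 and 55%, the 95% half-width is 1.96 × √(0.55 × 0.45 / 500) = 4.4 points. This is indicative only. The 500 is the nested study's case target (Synopsis, 4.9), and the size of the online cohort is not stated. A larger cohort would narrow the interval but leave the bias unchanged.

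**Selection within the invited routes.** The same formula applies to them. If the true prevalence were 55% and invitees with symptoms were 1.5 times as likely to respond (assumed), invited-only prevalence would be 64.7%, or 9.7 points too high before any advert respondent is added.

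**The case against.** The strongest reply is that the documents do not show inflation. A reader might infer that the primary estimate is too high because symptomatic people came through adverts. But the advert text is not shown, the self-referred share and any symptom excess are not given, and 4.2 makes the register the predominant source. That stands: the documents support a risk with a likely direction, not an established error.

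Second, adverts are not the only source of symptom-driven response. Register members volunteered for research and then choose whether to answer, and clinic-list patients also choose. This stands too, and the last calculation shows that the remaining bias could be larger than the advert component. A reader should not take an invited-only estimate as unbiased. Its advantage is a countable denominator.

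Third, it is too strong to say that no route is recorded anywhere. Clinic-list invitees are logged, an acceptance rate is a planned output of the screening log (7.2), and self-referrers contact the study team, who would know how they came. What stands is narrower: no route item is described in the questionnaire dataset, and no link from the log to that dataset is described for the whole cohort.

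Fourth, the primary analysis in 7.2 compares the current score of cohort and control, and controls may enter by the same routes, so part of the selection could cancel there. That limits the point to the prevalence. It does not remove it, since the Synopsis and section 3 make the proportion primary.

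Finally, weighting and sensitivity analyses may properly be left to the analysis plan, and their absence from the protocol is not criticised here. Capturing the route at entry cannot be left to it.

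**Conclusion.** The point holds as a limited one. The protocol makes a prevalence its primary outcome, admits advert-driven self-referral to a study named for Long COVID, pools all routes, and lists no route item in the cohort data. The prevalence is therefore at risk of upward selection bias that could not be assessed afterwards.

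The size is unknown. Under the assumed ranges it runs from 0.5 to 14.0 points, and it is zero without symptom-driven selection. The upper end needs a 50% self-referred share among COVID cases, which sits uneasily with a predominantly register-based cohort. Shares of 5% to 20% give 0.5 to 5.6 points. These figures rest on the assumed p, r and f and treat invited respondents as unselected, which they may not be.

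This is a cheap improvement worth making before further data are collected. It is not a demonstrated error in the result.

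**What to change.** - Issue a separate REDCap link for each recruitment route, or add a stored route field to the form, including for paper and telephone completion. Add the item to the data lists in 5.1 and 6.2.
- For the register and the list or record-search routes, report the number invited and the number responding.
- Report prevalence by route. State in advance an invited-only estimate (register plus list or record search), shown beside the pooled one.
- Say plainly that the invited-only estimate removes only the advert component of selection and that symptom-driven response among invitees remains.
- Keep self-referrers eligible for the nested study.

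Reweighting to overall SCI Diabetes counts is not recommended as the remedy. The primary question is conditional on infection, so all people with diabetes are the wrong target, and weighting by demographics does not correct response driven by symptoms.

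The cost is one extra field, a little more analysis, and a less precise invited-only estimate because it uses fewer people.
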